Grade 4 Total bilirubin > 10.0 x ULN	Discontinue study drug. Consider if hospitalization is appropriate.

Table 9. Recommended dose modifications and dose delays for suspected sonidegib** treatment-related toxicities	
Worst toxicity CTCAE grade*(value)	During a cycle of therapy
	AST or ALT
Grade 1 (> ULN - 3.0 x ULN)	Maintain dose level
Grade 2 (> 3.0 - 5.0 x ULN)	Maintain dose level
Grade 3 (> 5.0 - 20.0 x ULN)	Omit dose until resolved to ≤ Grade 1 or baseline then: •• If resolved in ≤ 7 days, then maintain dose level •• If resolved in > 7 days, then implement 50% dose reduction
Grade 4 (> 20.0 x ULN)	Omit dose until resolved to ≤ Grade 1 or baseline, then implement 50% dose reduction. Consider if hospitalization is appropriate
	Cardiac
Cardiac - prolonged QTc interval Grade 3 (QTcF > 500 msec or >60 ms from baseline on at least 2 separate ECGs taken within 1 hour)	First Occurrence: ◆ Omit dose ◆ Perform an analysis of serum potassium and magnesium, and if below lower limit of normal, correct with supplements to within normal limits. Concomitant medication usage must be reviewed. ◆ Perform a repeat ECG within one hour of the first QTcF of > 500 ms ◆ If QTcF remains > 500 ms, repeat ECG as clinically indicated but at least once a day until the QTcF returns to < 480 ms. ◆ Once QTcF prolongation has resolved, study treatment may be restarted with a 50% dose reduction Second Occurrence: ◆ discontinue patient from study drug

Cardiac - prolonged QTc interval	Discontinue patient from study drug
Grade 4	

Table 9. Recommended dose modifications and dose delays for suspected sonidegib** treatment-related toxicities	
Worst toxicity CTCAE grade* (value)	During a cycle of therapy
Otl	her Cardiac Events
Grade 1	Maintain dose level
Grade 2	Implement 50% dose reduction of buparlisib
Grade 3	Omit dose and discontinue study drug
Grade 4	Omit dose and discontinue study drug. Consider if hospitalization if appropriate
Oth	er adverse events**
Grade 1	Maintain dose level
Grade 2	Implement 50% dose reduction
Grade 3	Omit dose and discontinue study drug
Grade 4	Omit dose and discontinue study drug

Grade 3	Omit dose and discontinue study drug
Grade 4	Omit dose and discontinue study drug
	Consider if hospitalization if appropriate
111 1 110 1 1 1 1 1	i di

All dose modifications should be based on the worst preceding toxicity.

If the dose-limiting toxicity recurs in a patient following dose reduction, then further therapy with sonidegib will not be continued.

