Grade 3 Serum creatinine > 3.0 - 6.0 x ULN	Omit dose until resolved to ≤ Grade 1 then implement 50% dose reduction	
Grade 4 Serum creatinine > 6.0 x ULN	Omit dose and discontinue study drug. Consider hospitalization if appropriate	
Hepatic		
Bilirubin (*for patients with Gilbert syndrome these dose modifications apply to changes in direct bilirubin only) will be fractionated if elevated		

Total bilirubin <1.5 x ULN	Maintain dose level
T . 1177 1: 150 IV	Omit dose until resolved to \leq Grade 1, then:
Total bilirubin 1.5-3 x ULN	◆◆ If resolved in ≤ 7 days, then maintain dose level
	◆◆ If resolved in > 7 days, then implement 50% dose
	reduction
Condo 2	Ourit dans until manhand to < Conda 1 than
Grade 3	Omit dose until resolved to ≤ Grade 1, then implement 50% dose reduction
Total bilirubin > 3.0 - 10.0 x ULN	implement 30% dose reduction
Grade 4	Discontinue study medication
Total bilirubin > 10.0 x ULN	Consider if hospitalization is appropriate
	AST or ALT
Grade 1 (> ULN - 3.0 x ULN)	
	Maintain dose level
Grade 2 (> 3.0 - 5.0 x ULN)	Maintain dose level
Grade 3 (> 5.0 - 20.0 x ULN)	Omit dose until resolved to < Grade 1 or baseline then:
	♦♦ If resolved in \leq 7 days, then maintain dose level
	◆◆ If resolved in > 7 days, then implement 50% dose
	reduction
Grade 4 (> 20.0 x	Discontinue study drug
ULN)	Consider if hospitalization is appropriate
AST or	ALT and concurrent Bilirubin
AST or ALT > 3.0 x ULN and	Discontinue study drug
total bilirubin > 2.0 x ULN	

*(LFTs include albumin, ALT, AST, total bilirubin (fractionated if total bilirubin > 2.0 x ULN), alkaline phosphatase (fractionated if alkaline phosphatase is Grade 2 or higher) and GGT). Monitoring (*for patients with Gilbert Syndrome: total and direct bilirubin must be monitored, intensified monitoring applies to changes in direct bilirubin only; the monitoring includes the following LFTs: albumin, ALT, AST, total bilirubin (fractionated if total bilirubin > 2.0 x ULN), alkaline phosphatase (fractionated if alkaline phosphatase is Grade 2 or higher) and GGT).

In case of any occurrence of ALT/AST/ bilirubin* increase ≥ **Grade 2** the liver function tests must be monitored **weekly** or more frequently if clinically indicated **until resolved to** ≤ **Grade 1**

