	For non-fasting plasma glucose > 500 mg/dL (> 27.8 mmol/L) accompanied by signs/symptoms of hyperglycemia (for example, mental status changes, excessive thirst, polyuria), or presence of blood or urine ketones, discontinue buparlisib and following guidance for management of Grade 4 fasting plasma glucose (FPG).
	Cardiac
Cardiac - Left Ventricular systolic dysfunction	
Grade 1 or 2 Asymptomatic, resting ejection fraction 40-50%; or 10-20% drop from baseline	Reduce buparlisib dose by 50% Repeat LVEF within 4 weeks or as clinically appropriate
Table 10. Recommended dose modifications and dose delays for suspected buparlisib** treatment-related toxicities	
Worst toxicity CTCAE grade* (value)	During a cycle of therapy
Grade 3	Discontinue buparlisib
Symptomatic, ejection fraction responsive to intervention, ejection fraction 20-39% or > 20% drop from baseline	LVEF measurement to be repeated within 4 weeks or as clinically appropriate

Grade 4	Discontinue buparlisib
Refractory or poorly controlled heart	Hospitalize if appropriate
failure due to drop in ejection fraction;	Trospitalize ii appropriate
intervention such as ventricular assist	
device, intravenous vasopressor	
support or heart transplant indicated;	
ejection fraction < 20%	
*the event is considered resolved when	the patient is asymptomatic, has a resting ejection fraction
≥40% and ≤20% decrease from baseline	2 .
Cal	rdiac – QTc prolongation
Cardiac - prolonged QTc interval ≥	Refer to Table 9 Recommended dose modifications for
Grade 3 (QTcF > 500 msec	sonidegib.
or	Ç
>60 ms from	
baseline on at least 2 separate ECGs	
taken within 1 hour)	
	Other Cardiac Events
Grade 1	Maintain dose level
Grade 1	Maintain dose ievei
Grade 2	Implement 50% dose reduction of buparlisib
Grade 3	Omit dose and discontinue study drug
T 11 10 D	1 1 1 1 1 1 1 1 1 1 1 1 1 1 1 1 1 1 1 1
Table 10. Recommended dose modifications and dose delays for	
suspected dup	parlisib treatment-related toxicities
Worst toxicity CTCAE grade* (value)	During a cycle of therapy
-	
Grade 4	Omit dose and discontinue study drug
	Consider hospitalization if appropriate

Other	
Mood alteration	
* Mood questionnaire scores should be considered when assigning the AE Grade but psychiatric consult, if required, may determine the grade	

Grade 1	Maintain dose level

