Mild mood alteration (or Grade 2 anxiety if present at baseline)	Note : If question 9 (suicidal ideation) on the PHQ-9 has a positive response, or worsens in severity, the patient should be referred for psychiatric consult regardless of the total questionnaire score
Grade 2 Moderate mood alteration (for	Institute appropriate co-medication under the guidance of the psychiatrist. Maintain dose level.
Anxiety only, if worsened from baseline) and if there is no concurrent medical condition that accounts for an acute increase the PHQ score.	If the condition does not resolve to ≤ Grade 1 within 14 days despite medical treatment; then implement 50% dose reduction (continue to co-medicate) Note: If question 9 (suicidal ideation) on the PHQ-9 has a positive response, or worsens in severity, the patient should be referred for psychiatric consult regardless of the total questionnaire score
Grade 3	Discontinue study medication
Severe agitation; hospitalization not indicated	Note : If question 9 on the PHQ-9 has a positive response, or worsens in severity, the patient should be referred for psychiatric consult regardless of the total questionnaire score
Grade 4	Discontinue study medication. Consider hospitalization
Life-threatening consequences; urgent	if appropriate
intervention indicated	Note: If question 9 on the PHQ-9 has a positive response, or worsens in severity, the patient should be referred for psychiatric consult regardless of the total questionnaire score

Table 10. Recommended dose modifications and dose delays for suspected buparlisib treatment-related toxicities	
Worst toxicity	During a cycle of therapy
CTCAE grade* (value)	
Rash	
Grade 1 Macules /papules covering <10% BSA with or without symptoms (e.g. pruritus, burning)	Maintain dose level. Consider to initiate appropriate skin toxicity therapy (such as antihistamines, topical corticosteroids)

Grade 2 Macules/papules covering 10-30% BSA with or without symptoms; limiting instrumental ADLs	Reduce study drug dose to 50% of prior dose. Initiate/intensify appropriate skin toxicity therapy (such as antihistamines, topical corticosteroids)
Grade 3 Macules/papules covering >30% BSA with or without associated symptoms, limiting self-care ADLs	Discontinue study drug According to the investigators discretion, a paired skin biopsy could be obtained (from both an affected and an unaffected skin area for local histopathology assessment) if clinical appropriate

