Grade 4	Discontinue buparlisib. Consider if hospitalization is appropriate According to the investigators discretion, a paired skin biopsy could be obtained (from both an affected and an unaffected skin area for local histopathology assessment) if clinical appropriate.
Table 10. Recommended dose modifications and dose delays for suspected buparlisib** treatment-related toxicities	
Worst toxicity CTCAE grade* (value)	During a cycle of therapy
Fatigue (asthenia)	

Grade 1 Fatigue relieved by rest	Maintain dose level
Grade 2	Reduce study drug dose by 50% of prior
Fatigue not relieved by rest; limiting instrumental ADL	

Grade 3	Discontinue study drug
Fatigue not relieved by rest; limiting	
self care ADL	
Grade 4	Discontinue buparlisib.
	Consider if hospitalization is appropriate
	Pneumonitis
Please see Section 4.1.2.3.2; Table 14; 6.2.6.1.1.	and/or buparlisib Investigator Brochure Section
0	ther adverse events
Grade 1	Maintain dose level
Grade 2	Implement 50% dose reduction
Grade 3	Omit dose and discontinue study drug
Grade 4	Omit dose and discontinue
	study drug Consider if
	hospitalization if appropriate
	Other notes:
Table 10 Pesammen	
	ded dose modifications and dose delays buparlisib treatment-related toxicities
Worst toxicity CTCAE grade* (value)	During a cycle of therapy
Note: Omit dose for ≥ Grade 3 vomiting or Grade 3 nausea only if the vomiting or nausea cannot be controlled with optimal antiemetic	
All dose modifications should be based on the worst preceding toxicity.	
If the dose-limiting toxicity recurs in a patient following dose reduction, then further therapy with sonidegib will not be continued.	
If a patient requires a dose interruption of > 21 days from the intended day of the next scheduled dose because of a sonidegib-related toxicity, then the patient must be discontinued from the study.	
** Common Terminology Criteria for A	Adverse Events (CTCAE) version 4.03.

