5.1 Investigational treatment

For this study, the terms "investigational drug", "study drug" or "study treatment" refers to the combination of Sonidegib and buparlisib. If an individual drug is to be referenced the individual name will be present.

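### The stop rule for combined AST/ALT and bilirubin elevation appears only in the buparlisib table, so it is unclear whether sonidegib must also stop

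*Combined protocol and SAP*

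**What the plan says.** Table 9 in section 4.1 covers toxicity suspected to come from sonidegib, and Table 10 covers buparlisib. For overlapping hematologic, renal and hepatic toxicity, the text between the tables says that both drugs are reduced or stopped according to grade, each under its own table.

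Table 10 has a row headed AST or "ALT and concurrent Bilirubin". It applies when AST or ALT is above 3 x ULN and total bilirubin is above 2 x ULN, and its instruction is to "discontinue study drug". Table 9 has separate AST/ALT and bilirubin rows but none for the two together.

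For AST or ALT above 20 x ULN (Grade 4), Table 9 says: "Omit dose until resolved to ≤ Grade 1 or baseline, then implement 50% dose reduction. Consider if hospitalization is appropriate". Table 10 gives the same stop instruction as in its concurrent row.

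Section 5.1 says that *study drug* "refers to the combination of Sonidegib and buparlisib", and adds: "If an individual drug is to be referenced the individual name will be present".

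Table 10 does not keep to that convention. Its Grade 3 rash row reads "Discontinue study drug According to the investigators discretion, a paired skin biopsy could be obtained", while the Grade 4 rash row reads "Discontinue buparlisib. Consider if hospitalization is appropriate According to the investigators discretion". The fatigue rows switch in the same way. The Grade 4 glucose entry uses *study drug* for fasting values and names buparlisib for the matching non-fasting values.

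**The concern.** The two readings give different instructions for the same liver result. Under the section 5.1 definition, Table 10's concurrent row stops both drugs. Under the overlap rule, Table 10 governs buparlisib alone and sonidegib follows Table 9, where nothing recognises the combination as more serious than its parts.

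Both tables will usually apply. Section 4.3.3 attributes adverse events to the combination unless another cause is clear, and section 4.1 names hepatic toxicity as overlapping.

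The stake is patient safety: whether a patient who has raised transaminases together with raised bilirubin may be given sonidegib again, and at what dose. No sample size, response-rate definition or other statistical figure depends on the answer.

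**Working it through.** The plan states no figure to reproduce, so the check applies Table 9 to every result that meets Table 10's concurrent stop row.

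**Inputs, Table 9 (sonidegib), for values inside the concurrent row**
- AST/ALT >3 to 5 x ULN: keep the dose.
- AST/ALT >5 to 20 x ULN: hold; full dose if recovery takes 7 days or less, otherwise 50%.
- AST/ALT >20 x ULN: hold, then 50%.
- Bilirubin 1.5 to 3 x ULN (the part above 2 x ULN qualifies): hold; full dose if recovery takes 7 days or less, otherwise 50%.
- Bilirubin >3 to 10 x ULN: hold, then 50%.
- Bilirubin >10 x ULN: discontinue.

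**Grid.** Three AST/ALT bands by three bilirubin bands give 3 x 3 = 9 combinations. In each, the stricter of the two Table 9 rows is taken.

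| Sonidegib under Table 9 | Bilirubin >2–3 x | Bilirubin >3–10 x | Bilirubin >10 x |
|---|---|---|---|
| AST/ALT >3–5 x | full dose if ≤7 days, else 50% | 50% | stop |
| AST/ALT >5–20 x | full dose if ≤7 days, else 50% | 50% | stop |
| AST/ALT >20 x | 50% | 50% | stop |

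Stop: 3. Resume: 9 − 3 = 6. Of those 6, full dose is possible in 2 and 50% is the most allowed in 4. Table 10's concurrent row discontinues in all 9.

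**Worked case.** ALT 4 x ULN with bilirubin 2.5 x ULN. Table 9's ALT row keeps the dose. Its bilirubin row holds sonidegib and returns it to full dose if recovery takes 7 days or less. Table 10 discontinues.

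**Grade 4 AST/ALT alone.** ALT 25 x ULN with normal bilirubin. Table 9 restarts sonidegib at 50% after recovery. Table 10 discontinues: both drugs under the section 5.1 definition, buparlisib only under the overlap rule.

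**Does other text settle it?**
- Section 4.1 requires dosing adjustments to be discussed with the sponsor. That is a consultation, not a rule. After a dose-limiting toxicity it permits a 50% restart of either drug or both.
- The limits on interruptions longer than 21 days (section 4.1 and its tables, 4.1.1, 4.2.1) do not reach the two full-dose combinations, where recovery takes 7 days or less. Section 4.1 also has an exception for patients with clinical benefit. No sentence says whether a permanent stop of buparlisib counts as a delay.
- Section 3.1 describes combination treatment until progression, intolerable toxicity or withdrawal. It does not say whether one drug may go on alone.

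**The case against.** The strongest reply is that the overlap rule already answers the question. Table 9 is titled for sonidegib and Table 10 for buparlisib, and Table 10's rash, fatigue and glucose rows suggest that its authors wrote *study drug* when they meant buparlisib. A stricter liver rule for buparlisib is also reasonable, since section 1.5.2.2.1 singles out liver toxicity as a buparlisib side effect.

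There are safeguards too. Entry requires normal AST/ALT and bilirubin, with allowances for liver metastases and Gilbert syndrome. Liver tests are weekly after a Grade 2 or higher rise. A Table 9 footnote lets the investigator raise an unsuitable dose recommendation with the sponsor. The trial is single-center, so divergent practice is less likely.

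Much of this stands for Grade 4 AST/ALT alone. The better-supported reading there is that buparlisib stops and sonidegib may restart at 50%. A reader might infer that sonidegib must stop permanently as well; the documents do not require that, and it is a matter of clinical judgement.

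The reply does not rescue the concurrent row. If *study drug* in Table 10 means buparlisib, sonidegib has no concurrent rule at all, and the grid above follows.

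A reader might also see a third faulty rule in Table 9's Grade 3 febrile neutropenia row, which restarts sonidegib at 50% with no time limit. The documents do not support that. Such a patient has ANC below 1.0 x 10⁹/L and so also meets the Grade 3–4 neutropenia row in both tables, which discontinues if recovery takes more than 7 days. Taking the stricter row, as in the grid, removes most of the conflict.

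**Conclusion.** The concern holds for the concurrent row and, as a matter of terminology, for Grade 4 AST/ALT. Section 5.1 and the overlap rule in section 4.1 give conflicting answers on whether sonidegib stops when AST/ALT exceeds 3 x ULN with bilirubin above 2 x ULN. On the overlap reading, sonidegib can resume in 6 of 9 qualifying combinations, 2 of them at full dose. These are counts of table cells, not of patients, and they assume that the stricter Table 9 row governs each cell.

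How often this would arise cannot be calculated from the documents. A reader might turn to Table 6, which sums to 13 + 4 + 6 + 2 + 0 = 25 patients with Grade 3–4 liver toxicity out of 55 + 9 + 50 + 12 + 6 = 132. That figure covers all Grade 3–4 liver toxicity at buparlisib 100 mg, whatever its cause. It does not separate Grade 4 or concurrent elevations, and this trial gives 80 mg with sonidegib. It therefore does not measure how often the disputed rows would be triggered. With no Hy's law case reported so far, concurrent events are expected to be rare. The case for correction rests on how serious such an event would be and how little the correction costs.

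**What to change.** - Add the concurrent AST/ALT and bilirubin discontinuation row to Table 9, so that both drugs stop.
- In Table 10's Grade 4 AST/ALT row and its concurrent row, replace *study drug* with the drug or drugs meant.
- State in section 4.1 whether sonidegib may continue after buparlisib is permanently stopped.
- Minor: note in Table 9's Grade 3 febrile neutropenia row that the neutropenia row's discontinuation after more than 7 days also applies.

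The cost is amendment wording for these rows and one sentence in section 4.1, with no new data collection. The downside is that a few patients may stop sonidegib earlier than Table 9 now requires.

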In case of any occurrence of ALT/ AST/ bilirubin* increase \geq Grade 3 the liver function tests must be monitored weekly or more frequently if clinically indicated until resolved to \leq Grade 1; hereafter the monitoring should be continued every other week or more frequently if clinically indicated until the end of treatment with study medication.

Patients who discontinued study treatment should be monitored weekly, including LFTs* or more frequently if clinically indicated **until resolved to ≤ Grade 1 or stabilization** (no CTCAE grade change over 4 weeks).

Endocrine / Metabolic Fasting Plasma Glucose (FPG) during a cycle of therapy

Maintain dose level, check FPG every week initiate or intensify medication with appropriate anti-diabetic treatment as per investigator's discretion.

Instruct patient to follow dietary guidelines according to local and/or institutional standards for management of diabetes mellitus (such as those provided by the American Diabetes Association during the study.

Consider use of oral anti-hyperglycemic therapy such as metformin blood finger stick every day and if blood glucose levels are worsening for 2 consecutive days FPG assessment is recommended.

Check FPG at least weekly for 8 weeks, then continue checking at least every 2 weeks.

First occurrence:

If signs and symptoms of hyperglycemia (e.g. mental status changes, excessive thirst, polyuria), omit buparlisib immediately and manage as per Grade 3 hyperglycemia.

If asymptomatic, maintain dose and recheck FPG within 24 hours. If grade worsens to grade 3 or 4 follow specific Grade recommendations. If grade improves to grade 1 follow Grade recommendations. If FPG remains at Grade 2, reduce study drug dose to 50% of prior dose and check FPG every week initiate or intensify medication with appropriate anti-diabetic treatment as per investigator's discretion.

Instruct patient to follow dietary guidelines according to local and/or institutional standards for management of diabetes mellitus (such as those provided by the American Diabetes Association during the study.

Consider use of oral anti-hyperglycemic therapy such as metformin blood finger stick every day and if blood glucose levels are worsening for

2 consecutive days FPG assessment is recommended. Check FPG at least weekly for 8 weeks, then continue checking at least every 2 weeks.

Second occurrence:

Discontinue study drug

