Table 10. Recommended dose modifications and dose delays for suspected buparlisib treatment-related toxicities	
Worst toxicity CTCAE grade* (value)	During a cycle of therapy
_	
Grade 3 (> 250-500 mg/dL)	First Occurrence : Immediately omit buparlisib, initiate or intensify medication with appropriate

(> 13.9-27.8 mmol/L)	anti-diabetic treatment, recheck FPG within 24 hours. If Grade worsens to grade 4 then follow grade 4 recommendations. If Grade improves to grade 1 or 2 follow grade 1 or 2 guidelines. If FPG remains at Grade 3*:
	Administer intravenous hydration and intervention for electrolyte/ ketoacidosis/hyperosmolar disturbances as clinically appropriate
	Discontinue study drug Monitor FPG at least twice weekly until FPG resolves to ≤ Grade 1 Initiate or continue anti-diabetic treatment as appropriate Instruct patient to follow dietary guidelines according to local and/ or institutional standards for management of diabetes mellitus (such as those provided by the American Diabetes Association) during the study Consider use of oral anti-hyperglycemic therapy such as metformin Check FPG at least weekly for 8 weeks, then continue checking at least every 2 weeks
	For non-fasting plasma glucose >250-500 mg/dL (> 13.9 - 27.8 mmol/L) accompanied by signs/symptoms of hyperglycemia (for example, mental status changes, excessive thirst, polyuria), or presence of blood or urine ketones, omit buparlisib and following guidance for management of Grade 3 fasting plasma glucose (FPG)
	d dose modifications and dose delays parlisib** treatment-related toxicities
Worst toxicity CTCAE grade* (value)	During a cycle of therapy
	Discontinue study drug

Grade 4	Discontinue study drug
(> 500 mg/dL) (>27.8 mmol/L)	Consider hospitalization if appropriate.
	Initiate or intensify medication with appropriate anti- diabetic treatment, re-check within 24 hours, if grade
	improves then follow specific grade

	recommendations. If FPG is confirmed at Grade 4:
	Administer intravenous hydration and intervention for electrolyte/ ketoacidosis/hyperosmolar disturbances as clinically appropriate Instruct patient to follow dietary guidelines according to local and/or institutional standards for management of diabetes mellitus (such as those provided by the American Diabetes Association) during the study Consider use of oral anti-hyperglycemic therapy such as metformin. Check FPG at least weekly for 8 weeks, then continue checking at least every 2 weeks if clinically indicated

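### Table 10's Grade 4 fasting-glucose row orders a stop, then sends a patient who improves within 24 hours to rows that allow full or half dose

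*Combined protocol and SAP*

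**What the plan says.** All of this is in Section 4.1, Table 10, under fasting plasma glucose, unless another place is named.

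- **Grade 4 (above 500 mg/dL).** The first instruction discontinues study drug, with no condition attached. Anti-diabetic treatment follows, then "re-check within 24 hours, if grade", with the rule that an improved patient follows the recommendations of the specific grade. A second branch begins "If FPG is confirmed at Grade 4" and lists hydration, diet, metformin and FPG checks, with no dosing step.
- **Note under Grade 4.** For non-fasting glucose above 500 mg/dL with symptoms or ketones: "discontinue buparlisib and following guidance for management of Grade 4 fasting plasma glucose (FPG".
- **Grade 3 (above 250 to 500 mg/dL).** Buparlisib is first omitted. Then: "If Grade improves to grade 1 or 2 follow grade 1 or 2 guidelines". Study drug is discontinued only if FPG remains at Grade 3.
- **Grade 1.** "Maintain dose level, check FPG every week".
- **Grade 2, first occurrence.** If asymptomatic, the dose is kept and FPG re-checked within 24 hours; if FPG stays at Grade 2, "reduce study drug dose to 50% of prior" dose. If symptomatic, buparlisib is omitted and the patient managed as Grade 3. A second occurrence means discontinuation.
- **Closing note to Table 10.** "All dose modifications should be based on the worst preceding toxicity".
- **Section 5.1.** Study drug "refers to the combination of Sonidegib and buparlisib".

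The printed labels of the Grade 1 and Grade 2 rows are lost in the text available, but the wording of those rows identifies their grades. The Grade 4 label and text are intact.

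**The concern.** A patient whose FPG falls from above 500 mg/dL to a lower grade within a day of anti-diabetic treatment meets two instructions in the same row: stop, and follow a row whose dosing step continues treatment. The row does not say which governs. Section 4.1.2.2 tells investigators to adhere to Table 10 for glucose disturbances, so this is operative text. At stake is re-exposure, possibly at full dose, after the most severe hyperglycemia grade that the table lists. It is a safety-rule inconsistency and affects no planned analysis.

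**Working it through.** The plan states no figure on this point, so the first part is a comparison of text and the second gives the scale.

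**Paths that the row allows, read literally**

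| FPG at the 24-hour re-check | Dosing step reached |
|---|---|
| Still Grade 4 | Stop (first line of the row) |
| Grade 3 | Omit and re-check; then the Grade 1 or 2 rows if improved, or discontinue if still Grade 3 |
| Grade 2, symptomatic | Omit and manage as Grade 3 |
| Grade 2, asymptomatic, first occurrence | Full dose pending re-check, then 50% if it persists |
| Grade 1 | Full dose |

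Every line below the first conflicts with the unconditional stop. The last two lead directly to continued dosing.

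**Which instruction the table favours**

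1. The Grade 3 row uses *omit* for a temporary hold and keeps *discontinue* for failure to improve. The Grade 4 row uses *discontinue* at once, before the re-check. It does not naturally read as a hold.
2. The closing note ties dose changes to the worst preceding toxicity, here Grade 4. It does not decide the matter alone, because the Grade 3 row sits under the same note and still routes patients downward.
3. The other Grade 4 rows of Table 10 for creatinine, bilirubin, AST/ALT, left ventricular function, other cardiac events, mood, rash, fatigue and other adverse events all discontinue, with no route back. Grade 4 neutropenia and platelets are held, with return at no more than 50%. No other Grade 4 row there permits a full-dose return.
4. The order of severity is inverted: a second Grade 2 occurrence means discontinuation, while Grade 4 falling to Grade 1 could mean full dose.
5. Section 4.1's rule for dose-limiting toxicity (DLT) allows a restart at a 50% reduction, and Section 4.1.2.2.1 speaks of resuming at a lower dose. Both weigh against a full-dose return and say no more than that.

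**How often the row would be used**

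Inputs: the 100 mg patients in Table 8 (Section 1.5.2.2.1), and the statement in that section that the only two Grade 4 cases were both at 150 mg/day. I assume that this statement covers the studies in Table 8.

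- Patients at 100 mg: 55 + 9 + 50 + 12 + 6 = 132, with 0 Grade 4 events.
- One-sided 95% upper limit: 1 − 0.05^(1/132) = 2.24%.
- Expected events in the planned 24 patients at that limit: 24 × 0.0224 = 0.54.
- Leaving out the one study that admitted controlled diabetes: 132 − 50 = 82; 1 − 0.05^(1/82) = 3.59%; 24 × 0.0359 = 0.86.

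None of the five studies added sonidegib, so these limits are not hard ceilings. The 80 mg dose, the entry FPG limit of 120 mg/dL and the exclusion of poorly controlled diabetes point to a lower rate.

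**The case against.** The best defence is that the row does not contradict itself. The stop stands above both branches, and the branch for confirmed Grade 4 contains no dosing step. On that view dosing is already settled, and the re-check only selects the level of glucose care. This is a fair reading, and the fix below writes it out. But the row does not limit its routing to glucose care, and the Grade 1 row it points to opens with a dosing instruction, so the ambiguity stands.

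The opposite defence is that the stop awaits confirmation at 24 hours. The stop comes before the re-check, and the table has a different word for a hold. If that was the intent, the row still needs rewording.

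It is also fair that the harmful path is long. FPG must fall from above 500 mg/dL to Grade 1 or asymptomatic Grade 2 in a day, although buparlisib's effective half-life is about 40 hours (Section 1.5.2.1). The investigator must then pass over the first line, and Section 4.1 has dosing adjustments discussed with the sponsor. These points limit the size of the problem but do not say which instruction governs.

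Three stronger readings are not supported:

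- *Sections 4.1 and 4.1.2.2.1 require a permanent stop.* They describe resumption at a reduced dose, and the documents do not define a DLT in a way that shows Grade 4 FPG is one.
- *Both drugs must stop, because Section 5.1 defines study drug as the combination.* Section 4.1 says an event clearly due to one drug follows that drug's adjustment. Section 1.5.2.2.1 calls hyperglycemia an on-target buparlisib effect. The overlapping toxicities for which Section 4.1 acts on both drugs are hematologic, renal and hepatic.
- *There is a 42% chance of wrongful re-dosing.* The figure 1 − (1 − 0.0224)^24 = 42% is the chance of at least one Grade 4 event of any course in 24 patients, and only if the true rate sat at the upper limit.

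**Conclusion.** The inconsistency is real and lies in intact text. The Grade 4 row orders an unconditional stop, then routes an improved patient to rows that permit full or half dose. The choice of *discontinue* over *omit*, the worst-toxicity note and the other Grade 4 rows that discontinue all favour stopping.

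The practical size is small: about 0.5 Grade 4 events expected in 24 patients at the 2.2% upper limit, or 0.9 at the 3.6% limit. These figures rest on monotherapy and other combinations at 100 mg, carried over to 80 mg with sonidegib. Improvement followed by wrongful re-dosing must be less frequent than Grade 4 itself; the documents give no rate for it. This is a worthwhile wording correction and no threat to the trial's conclusions.

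**What to change.** Reword the Grade 4 FPG row along these lines:

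*Discontinue buparlisib; do not resume if the grade improves. Re-check within 24 hours; if the grade improves, follow only that grade's glucose-care and monitoring steps, not its dosing steps.*

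The care list for confirmed Grade 4 and the non-fasting note can stay as they are; that note already names buparlisib. Sonidegib is then handled under Section 4.1's single-drug rule. Two clarifications belong with the change: that this row takes precedence over the 50% restart in Section 4.1's DLT rule, and whether Section 4.2.1's rule, which ends all treatment after a buparlisib delay of more than 21 days, applies to a patient stopped under this row.

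The change touches one table row, with no effect on sample size or visits. Its price is that a patient with a single transient or erroneous value above 500 mg/dL loses buparlisib. Such a patient stays in the Full Analysis Set (Section 6.1), so one stop can move a 12-patient cohort's response rate by at most 1/12 = 8.3 percentage points.
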